Pilot RCT of Patient Centered eHealth Intervention for Nonadherent HIV+ Substance Users. NCT Unique protocol ID 18938. Document Date Oct 31, 2022

Pos4Health Statistical Analysis Plan

1. Is stratification/randomization involved? Yes, Randomization

► IF YES, describe the stratification/ randomization scheme.

Randomization will be achieved using a random number generator. Equal numbers of participants will be assigned to the two arms. The participants will be blinded to the randomization. Because the consent form describes the two arms, it is possible that participants will deduce which treatment arm they are in. The statistician will generate randomization for the participants. The project coordinator will remain blind to the randomization until it is time to randomize participants (after study consent and TLFB). At that point, the coordinator will learn which treatment that participant will receive and will provide participants with the instructions relevant to their assigned conditions. Co-investigators will have access to the randomization.

► IF YES, who will generate the randomization scheme?

UVa Statistician. [name]

2. What are the statistical considerations for the protocol?

Study Design: 2 group (experimental and control) pilot RCT with assessments at pre-treatment and post-treatment, with a focus on assessing feasibility and acceptability, along with preliminary efficacy.

1. Endpoints and precision estimates for feasibility: Feasibility will be judged by the rates of study acceptance and completion of the trial. Study Acceptance will be determined by consents obtained divided by patients approached for the study. *We will judge this trial feasible if the acceptance rate among eligible patients is equal to or greater than 56%*. This cut-off was chosen so that if we meet this criterion, we can be 95% certain that the population proportion of acceptance is at least 50%. We will interview a subset of participants who completed the intervention. Completion rate will be n completed follow-up interviews divided by n baseline interviews. *We will judge a larger scale trial feasible if our completion rate at the 3M follow-up is 80%*. This decision rule was chosen so that if it is met, we can be 95% certain that the proportion of patients for whom this is feasible is at least 75%.
2. Endpoints for Acceptability: We will judge acceptability by participant ratings, and by actual program usage data. Participants will rate the Intervention at follow-up. The range of items on this scale is from 1 to 7. An item mean of 3.5 would be mid-range. Basic descriptive information will be gathered from the tracking system about whether participants logged in, how many times, and for how long. Time spent in each Core will be tracked and summarized. We will judge *eHealth Positive* acceptable if if the average score on the evaluation was ≥ 5.6 , which is 80% of the highest score (range 1-7), and if 75% of participants completed at least half of the Cores and provide 4 of 7 daily diaries of adherence on at least 4 weeks.

Pilot RCT of Patient Centered eHealth Intervention for Nonadherent HIV+ Substance Users. NCT Unique protocol ID 18938. Document Date Oct 31, 2022

3. Endpoints for preliminary efficacy components: PRIMARY: HIV viral suppression rates for the experimental vs. control group SECONDARY: adherence (6M average pharmacy refill rate), retention in care (6M missed visit proportion), and substance using days per 30 day period. Because this is a pilot study, we are not estimating power and precision, but rather, gathering information on effect size to assist in estimating power for a subsequent definitive trial.

Pilot Study, no early stopping, no interim analyses, no stratification.

3. Provide a justification for the sample size used in this protocol.

Because this is a pilot study, we are not estimating power and precision, but rather, gathering information on effect size to assist in estimating power for a subsequent definitive trial. Rather, in our experience with pilot trials of behavioral interventions, and of Internet interventions, an n of 25 per group is usually sufficient for detecting a signal and for estimating effect size. As detailed above, we may consent 100 participants to get 71 fully enrolled and an n of 50 (25 per group) with all data available for analysis.

4. What is your plan for primary variable analysis?

Primary research questions and analytic approach:

1. **Is the intervention trial feasible?** The main reason to conduct this project is to develop a feasible intervention to prepare for a randomized trial. Feasibility standards are based on a synthesis of criteria for behavioral research trials.¹³¹ Feasibility will be judged by the rates of study acceptance and completion of the trial. Study Acceptance will be determined by consents obtained divided by patients approached for the study. *We will judge this trial feasible if the acceptance rate among eligible patients is equal to or greater than 56%*. This cut-off was chosen so that if we meet this criterion, we can be 95% certain that the population proportion of acceptance is at least 50%. We will also evaluate factors that influence some eligible candidates to refuse participation (Study Refusal). We will query eligible refusers about the recruitment process, the informed consent process, the study description, how they learned about the study, and other factors, to learn how these might be improved. Some who enroll will not complete the study (Dropout). We will ask dropouts about the time commitment, difficulties understanding the study, problems with the web program or their device, privacy concerns, or other reasons they discontinued participation. We will interview a subset of participants who completed the intervention to permit comparisons of refusers vs. enrollers and completers vs. dropouts. Completion rate will be n completed follow-up interviews divided by n baseline interviews. *We will judge a larger scale trial feasible if our completion rate at the 3M follow-up is 80%*. This decision rule was chosen so that if it is met, we can be 95% certain that the proportion of patients for whom this is feasible is at least 75%.
2. **Is the intervention acceptable?** We will judge acceptability by participant ratings, and by actual program usage data. Participants will rate the Intervention at follow-up. The range of items on this scale is from 1 to 7. An item mean of 3.5 would be mid-range.

Pilot RCT of Patient Centered eHealth Intervention for Nonadherent HIV+ Substance Users. NCT Unique protocol ID 18938. Document Date Oct 31, 2022

Basic descriptive information will be gathered from the tracking system about whether participants logged in, how many times, and for how long. Time spent in each Core will be tracked and summarized. We will judge *eHealth Positive* acceptable if if the average score on the evaluation was ≥ 5.6 , which is 80% of the highest score (range 1-7), and if 75% of participants completed at least half of the Cores and provide 4 of 7 daily diaries of adherence on at least 4 weeks.

- 3. Does eHealth Positive show promise, showing impact on knowledge and usage of coping strategies? Preliminary efficacy.** To assess the promise of Pos4Health, we will test it in a pilot RCT among 50 nonadherent PLWH recruited from throughout the South, Virginia, and the United States--particularly areas with rural and nonurban occupants. The study will compare Pos4Health to a static Patient Education website for its impact on the primary outcome of viral suppression rate. Additionally, to inform a subsequent RCT, we will record the impact on secondary outcome variables of adherence (6M average pharmacy refill rate), retention in care (6M missed visit proportion), and on substance using days per 30 day period. The pilot test will also provide data on varied types of substance users, allowing some basic comparisons between non-injection and injection drug users, or between drinkers and drug users. While this pilot study will not be powered for direct statistical comparisons, we will examine the data for each primary and secondary outcome by these groups. If the data indicate potential differences, we will examine these in simple regression analyses. Data will be collected in person and through the web program, and electronically from the electronic medical records of clinics and pharmacies. We will characterize the data using standard methods (means, medians, standard deviations, confidence intervals). Prior to analyses, psychometric analyses will be conducted to assess reliability of the measures and to adjust for abnormal distributions. We will also characterize patterns of missing data. Paired t- tests will compare change over time from baseline to post-treatment follow-up. We anticipate the use of nonparametric tests to allow for non-normality. Linear regression models will be used to adjust for effects of relevant covariates on participant responses over time. We will assess the magnitude of associations among the outcome variables using Pearson's correlation coefficients.

5. What is your plan for secondary variable analysis?

Secondary research question and analytic approach:

How do adherence and engagement in care measures perform as future primary outcomes? Obviously, the ultimate goal for the intervention is to improve adherence and engagement in care, although we will not answer this definitively in this pilot trial. At this stage, we will examine the data quality of adherence and engagement in care indicators (Pharmacy Refill Rate, Missed Visit Proportion) to determine which ones are suitable as outcome measures in a future RCT. *The purpose is to calculate effect sizes for the planned randomized trial.*

6. Have you been working with a statistician in designing this protocol? YES

IF YES, what is their name? [name]

Pilot RCT of Patient Centered eHealth Intervention for Nonadherent HIV+ Substance Users. NCT Unique protocol ID 18938. Document Date Oct 31, 2022

7. Will data from multiple sites be combined during analysis? NO

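### Meeting the 80% completion rule does not give 95% certainty of at least 75% completion at any size the SAP states (50, 71 or 100)

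*SAP*

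**What the plan says.** The feasibility rule appears in the SAP under question 2, item 1 (endpoints and precision estimates for feasibility) and again under question 4, item 1:

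- **The rule:** "We will judge a larger scale trial feasible if our completion rate at the 3M follow-up is 80" percent.
- **The reason given for it:** "we can be 95% certain that the proportion of patients for whom this is feasible is at least 75" percent.
- **The denominator:** "Completion rate will be n completed follow-up interviews divided by n baseline interviews".

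No number of baseline interviews and no interval method accompany the statement. The only sizes in the SAP are in the sample-size justification (question 3): "we may consent 100 participants to get 71 fully enrolled and an n of 50 (25 per group) with all data available for analysis".

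The SAP also says "Because this is a pilot study, we are not estimating power and precision". That sentence stands with the preliminary efficacy endpoints (question 2, item 3) and in the sample-size justification (question 3), not with the feasibility rules.

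**The concern.** The gap between the cut-off (80%) and the assured value (75%) is only five percentage points. A lower confidence limit that close to the observed proportion needs a fairly large sample, and this is a pilot of at most 100 consented participants.

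Completion is one of only two feasibility criteria, and feasibility is the first of the SAP's primary questions. A reader who sees the rule met would believe that retention of at least 75% had been shown with 95% confidence. If the data support only a lower figure, the attrition allowance for the larger trial could be set too small.

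**Working it through.** **Inputs**

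- Cut-off 80%, confidence 95%, assured value 75%: SAP question 2, item 1, repeated in question 4, item 1.
- Candidate denominators 50, 71 and 100: SAP question 3.
- Readings adopted: the rule is met at 80% or more, and the 95% certainty is a one-sided 95% lower limit. The one-sided reading is more favourable to the SAP than a two-sided one.

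The assurance is promised whenever the rule is met, so it must hold at the smallest passing count: 40/50 (80.0%), 57/71 (80.3%) and 80/100 (80.0%).

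**Step 1. Try to reproduce the 75%**

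Wald lower limit = p − 1.645 × √(p(1 − p)/n).

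- 40/50: 0.800 − 1.645 × √(0.16/50) = 0.800 − 1.645 × 0.0566 = 0.707
- 57/71: 0.803 − 1.645 × 0.0472 = 0.725
- 80/100: 0.800 − 1.645 × 0.0400 = 0.734

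The exact (Clopper-Pearson) limit is the 5th percentile of a Beta(x, n − x + 1) distribution. With the Wilson limit added:

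| Count | Wald | Wilson | Exact |
|---|---|---|---|
| 40/50 | 70.7% | 69.3% | 68.4% |
| 57/71 | 72.5% | 71.5% | 70.9% |
| 80/100 | 73.4% | 72.7% | 72.3% |

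None reaches 75%. Two-sided 95% intervals have lower limits still (exact: 66.3%, 69.1%, 70.8%).

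**Step 2. The confidence actually attained**

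If true completion is exactly 75%, a rule giving 95% certainty should be met no more than 5% of the time. The binomial probabilities are:

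- P(X ≥ 40 | n = 50, p = 0.75) = 0.262
- P(X ≥ 57 | n = 71, p = 0.75) = 0.188
- P(X ≥ 80 | n = 100, p = 0.75) = 0.149

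One minus these is the attained exact confidence: 74%, 81% and 85%. The Wald equivalent, Φ((p − 0.75)/SE), gives 81%, 87% and 89%. A Bayesian reading with a uniform prior gives posterior probabilities of 76%, 83% and 86% that completion is at least 75%.

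**Step 3. The size at which the statement would hold**

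With an observed rate of exactly 80%, the Wald limit reaches 75% when n = 1.645² × 0.16 / 0.05² = 173.2, so about 174. By Wilson it takes about 205 (164/205 gives 75.03%) and by the exact method about 220 (176/220 gives 75.04%).

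Rounding the passing count up to the next whole person, as in step 1, helps at some sizes. On that convention 75% is first reached at 139 (Wald), 174 (Wilson) or 189 (exact). All of these exceed 100.

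**Step 4. The cut-off that would support 75% at the stated sizes**

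The smallest counts with an exact limit of at least 75% are 43/50 (86%), 60/71 (84.5%) and 83/100 (83%). If true completion is 80%, the chance of passing is then:

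| n | Present 80% rule | Raised cut-off |
|---|---|---|
| 50 | 58% | 19% |
| 71 | 55% | 21% |
| 100 | 56% | 27% |

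**The case against.** - **The SAP disclaims precision.** It does so for efficacy and for the sample size. The feasibility item is itself headed as giving precision estimates and makes an explicit 95% claim, so the disclaimer does not withdraw it.
- **The cut-off has another basis.** Question 4, item 1 says the feasibility standards draw on a synthesis of published criteria. That is a fair reason to keep 80%. It concerns feasibility standards in general, though; the 95%/75% sentence is the only reason tied to the 80% figure itself.
- **Fifty is a doubtful denominator.** This stands in part. Question 3 describes 50 as those with complete data, which reads as a count after losses. On the other hand, question 4, item 3 describes the pilot as a trial among 50, so 50 cannot be excluded. The largest discrepancies come from n = 50. At 71 and 100 the shortfall from 75% is about 2 to 4 percentage points, and the claim still fails.
- **The exact limit is the most conservative of the three methods.** True, and the SAP names none. The most lenient method at the largest stated size still gives only 73.4%.
- **The consequence for planning is inferred.** This also stands. The SAP does not say that 75% will be carried forward. The inference is modest, because the rule exists to judge whether a larger trial is feasible.

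**Conclusion.** The statement is wrong as written. At the threshold, an observed 80% supports a true completion rate of about 68% to 72% (exact) or 71% to 73% (Wald) with 95% confidence, not 75%. The confidence attached to 75% is about 74% to 85% (exact) or 81% to 89% (Wald), depending on which stated size is the denominator.

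This rests on reading the rule as 80% or more, the certainty as a one-sided 95% lower limit, and the number of baseline interviews as one of the three sizes in the SAP. No choice among those sizes, and no standard interval method, rescues the claim. The 80% rule itself remains usable; what fails is the assurance attached to it. It should be corrected because it supports a primary feasibility decision, but it does not stop the trial or change any analysis.

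**What to change.** In question 2, item 1 and question 4, item 1:

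1. Keep the rule, worded as 80% or more.
2. State the planned number of baseline interviews.
3. Replace the 95%/75% sentence with the assurance at that number, naming the interval method. For example: *With 71 baseline interviews, meeting the 80% rule gives 95% confidence (one-sided exact limit) that true completion is at least about 71%.* The figure is about 68% with 50 baseline interviews and about 72% with 100.
4. Report the observed completion rate with its one-sided 95% exact lower limit at the actual number of baseline interviews.

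This changes SAP wording only; its cost is a somewhat less favourable stated assurance. Raising the cut-off so as to keep the 75% claim is also open to the sponsor. The price is shown in step 4 of the working: a trial with true completion of 80% would pass only about one time in four or five, where it now passes somewhat more than half the time.

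### Does planning for 50 complete data sets from 71 enrolled (70%) contradict the 80% completion criterion?

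*SAP*

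**What the plan says.** Section 3 (sample size) makes no power calculation. It takes its target from the team's experience, that "an n of 25 per group is usually sufficient for detecting a signal and for estimating effect size", and gives a recruitment funnel: "we may consent 100 participants to get 71 fully enrolled and an n of 50 (25 per group) with all data available for analysis". Section 1 adds that "Equal numbers of participants will be assigned to the two arms".

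The feasibility rule stands in section 2, item 1, and is repeated in section 4, item 1. The measure is defined by interviews: "Completion rate will be n completed follow-up interviews divided by n baseline interviews". The threshold is "We will judge a larger scale trial feasible if our completion rate at the 3M follow-up is 80" per cent.

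The outcomes reach beyond that interview. Besides viral suppression, section 2, item 3 lists "adherence (6M average pharmacy refill rate), retention in care (6M missed visit proportion), and substance using days per 30 day period". On sources, section 4, item 3 states: "Data will be collected in person and through the web program, and electronically from the electronic medical records of clinics and pharmacies".

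The SAP gives no attrition rate. It does not say that 71 is the number of baseline interviews, or that 50 is the number of 3-month interviews expected.

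**The concern.** The step from 71 to 50 is the only figure in the SAP for losses after enrolment, and it lies about ten percentage points below the completion threshold. If the 71 are the people with a baseline interview and the 50 are those interviewed at 3 months, the sponsor has planned for a rate that fails its own test. Either the loss allowance would then be too pessimistic, with more people enrolled than the target needs, or the criterion would be one the team does not expect to meet.

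This would matter in a pilot whose stated main purpose is feasibility and which disclaims power. The completion rule decides whether a larger trial is judged feasible. If it were unclear which count enters the numerator, the result could be argued either way afterwards.

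**Working it through.** **Inputs.** From section 3: 100 consented, 71 fully enrolled, 50 with all data (25 per group). From section 2, item 1: threshold 80%, defined as follow-up interviews over baseline interviews. Treating 71 as the denominator is an assumption.

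**The plan's own funnel.** The ratios are 71/100 = 71.0% and 50/71 = 70.4%. An allowance of 29% at each step (inferred, not stated) reproduces it: 50/(1 − 0.29) = 70.4, rounded up to 71, and 71/(1 − 0.29) = 100. The arithmetic contains no error.

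**What the 80% rule needs.** 0.80 × 71 = 56.8, so 57 interviews (57/71 = 80.3%; 56/71 = 78.9% falls short). The figure of 50 is 7 below this.

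**Chance of meeting the rule.** With X binomial (71, p), P(X ≥ 57) is:

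| True 3-month interview rate p | P(X ≥ 57) |
|---|---|
| 50/71 = 70.4% | 4.2% |
| 75% | 18.8% |
| 80% | 54.7% |
| 85% | 89.6% |

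The 4.2% applies only if the complete-data rate and the interview rate are the same quantity.

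**Can both figures hold?** Yes. If 57 of 71 give the 3-month interview (80.3%) and 50 of those 57 (87.7%) also have all other data, the criterion is met and the analysis set is 50. This requires 7 interviewed participants to lack some other item, such as a 6-month refill or missed-visit figure.

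**Is 71 too many if 80% is expected?** Deriving enrolment from 80% gives 50/0.80 = 62.5, so 63. Let Y be the number with complete data, binomial (n, p):

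| True complete-data rate | P(Y ≥ 50), n = 71 | P(Y ≥ 50), n = 63 |
|---|---|---|
| 75% | 85% | 26% |
| 80% | 98% | 62% |

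Enrolling 63 reaches the target on average but leaves a substantial chance of falling short. Enrolling 71 is what a planner who hoped for 80% and wanted a margin might choose.

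**The case for a change.** The strongest case for a change is that the SAP never states the reading that reconciles the figures. Section 4 names dropout as the loss after enrolment and contrasts completers with dropouts. It gives no rate of missing record data among completers and says only that patterns of missing data will be characterised. The funnel sentence refers back to detail that does not appear earlier in this SAP. Section 4, item 3 describes the pilot as being among 50 people, which leaves open whether 50 is the whole trial or its complete-data subset. The denominator is not pinned down either: if some people give a baseline interview without becoming fully enrolled, it exceeds 71 and 50 falls further below the threshold. A few sentences would settle all this at no cost in patients.

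What stands is that the two figures are not linked, and that a reader cannot tell from the SAP how many 3-month interviews are expected. A stated expectation (at least 57 if 71 is the denominator) would have been helpful.

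What does not stand is the step from there to an error. The completion rate has a written numerator and denominator, both counts of interviews, so the size of the complete-data set does not enter it. The funnel is worded as something the team may do, which suits an allowance better than a forecast. A cautious allowance can sit below a demanding criterion without contradiction. The criterion also concerns a larger trial, so missing it would be a finding of the pilot rather than a failure built into it.

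**Conclusion.** No change to the plan follows. The gap between 70.4% and 80% is real as arithmetic, but it compares a complete-data fraction with an interview-completion fraction. The two conflict only if 71 is the number of baseline interviews and 50 the number of 3-month interviews expected. The SAP states neither, and its 6-month and record-based outcomes give a ready reason for the complete-data count to be smaller.

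Analysts following the SAP as written would enrol up to 71, count the baseline and follow-up interviews, and set the observed rate against 80%. That result is the same whatever rate was assumed when the recruitment target was chosen. Nor is 25 per group misstated: it is a target based on experience, and ending with more would simply exceed it. Cutting enrolment to 63 would bring no clear gain, because at 80% complete data it lowers the chance of reaching 50 from 98% to 62%.

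What remains is an unstated link between a recruitment allowance and a decision rule. These probabilities assume independent participants with a common rate, and the 57-of-71 figure assumes that 71 is the denominator. The conclusion depends on neither, since the rule is applied to observed interview counts.

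### Does the SAP confine the efficacy comparison to the 50 participants with complete data?

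*SAP*

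**What the plan says.** Item 3 (sample size) declines a power calculation because this is a pilot, cites experience for 25 per group, and then gives the expected flow: up to 100 consented to reach "71 fully enrolled and an n of 50 (25 per group) with all data available for analysis". Item 4, question 3 (preliminary efficacy) repeats the number: "we will test it in a pilot RCT among 50 nonadherent PLWH".

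Item 1 places randomization after consent and the TLFB and says "Equal numbers of participants will be assigned to the two arms". Item 2 states the primary efficacy endpoint as viral suppression in the experimental versus the control group. The secondary endpoints are refill rate, missed visits and substance-use days.

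The provision for incomplete data in item 4, question 3 is one sentence: "We will also characterize patterns of missing data". The same paragraph names paired t-tests for change from baseline, nonparametric tests, linear regression with covariates and Pearson correlations. It also lists electronic clinic and pharmacy records among the data sources. Nowhere does the SAP define an efficacy analysis set.

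**The concern.** The only number attached to the efficacy comparison is 50, and it is tied to having all data. With no set of all randomized participants named, and no handling of missing values beyond description, an analyst could take the 50 as the analysis set and compare completers.

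That would matter because the efficacy part exists to give an effect size for planning the definitive trial. If loss occurs after randomization, is related to outcome and differs between arms, the completer difference is biased and the bias passes into the next sample size.

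The SAP's own text makes such loss plausible. Item 4, question 1 says "We will ask dropouts about the time commitment, difficulties understanding the study, problems with the web program or their device", and the arms use different programs: "The study will compare Pos4Health to a static Patient Education website". In nonadherent substance users, a link between dropping out and viral suppression, refills or visits is easy to believe.

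**Working it through.** **1. What kind of number is the 50?** The SAP states no attrition rate, so I solved for one. With N/(1 − d) and d = 0.29:
- 50/0.71 = 70.4, rounded up to 71
- 71/0.71 = 100

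One rate applied twice reproduces the whole 100–71–50 chain. The 80% completion criterion does not: 50/0.80 = 62.5, rounded up to 63. The chain therefore looks like ordinary recruitment inflation, worked back from 25 per group. It does not look like a rule about who is analysed.

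**2. How much loss could follow randomization?** The upper limit is 71 − 50 = 21, or 21/71 = 29.6%. The lower limit is zero, if the 50 are those randomized, as item 4, question 3 can be read. Item 1 puts randomization soon after consent, which points towards some later loss. The number is not settled here and may be in the protocol.

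**3. What would a completer comparison cost?** Let k be the number lost after randomization, with 50 observed, the same loss fraction f = k/(50 + k) in each arm, and the same true rate p. An arm whose lost participants have suppression q shows (p − f·q)/(1 − f). The spurious arm difference is f/(1 − f) = k/50 times the arm difference in q.

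| k | multiplier | 10-point difference among those lost | 20-point difference among those lost |
|---|---|---|---|
| 0 | 0 | 0 | 0 |
| 10 | 0.20 | 2.0 points | 4.0 points |
| 21 | 0.42 | 4.2 points | 8.4 points |

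Example at k = 21, p = 50%, q = 30% versus 50%: (0.50 − 0.2958 × 0.30)/0.7042 = 58.4%, against 50.0%.

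Unequal loss can do more. Assume arms of 36 and 35, 15 suppressed in each, and everyone lost unsuppressed. As assigned, 15/36 − 15/35 = 41.7% − 42.9% = −1.2 points. With 22 and 28 completers, 15/22 − 15/28 = 68.2% − 53.6% = +14.6 points. With 20 and 30, 75% − 50% = +25 points.

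All these inputs beyond the 71 and 50 are assumed. For scale, the 95% half-width at 25 per arm and rates near 50% is 1.96 × √(0.25/25 + 0.25/25) = 27.7 points.

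**4. Does the text prescribe that comparison?**
- The sentence with the 50 answers a request to justify the sample size and is worded as an expectation. It leaves out nobody who has an outcome.
- The paired t-tests compare a person with himself or herself over time. They do not compare the arms, so they do not define who enters the arm comparison.
- Linear regression drops a record only if a variable in that model is missing. This gives an available-case analysis for each outcome, which is wider than the set complete on everything.
- The primary endpoint is stated by group, and nothing reassigns or removes participants.
- Clinic and pharmacy records are already a source. Refill rate and missed visits, and plausibly viral load, could be had from them without a follow-up interview. The SAP does not map outcomes to sources, so this is likely but not proved.

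**5. Would a written missing-data rule repair the rest?** Only partly. For a participant whose outcome cannot be obtained, naming the set creates no data. Counting missing as not suppressed has its own error: with 50% true suppression in both arms and random missingness of 20% versus 40%, it gives 0.50 × 0.80 = 40% against 0.50 × 0.60 = 30%, a spurious 10 points. That exceeds the largest value in the equal-loss table.

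**The case for a change.** The strongest reply is that an analysis set and a rule for incomplete records belong in a SAP, so their absence cannot be left to the protocol. The pilot's lack of power is no defence either, since the estimate itself is the product and a wide interval does not remove a systematic error. The text also leans towards loss after assignment, and the SAP never says that record-based outcomes of dropouts will be used.

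Much of this stands. The SAP is silent on the set, the arithmetic of the possible bias is sound, and I do not rely on the 27.7-point half-width to dismiss it. What does not stand is the step from silence to a completer analysis. The sentence that carries the number is a forecast, the methods do not impose that set, and a planned data source works against it.

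**Conclusion.** No change to the plan is needed. The SAP leaves a detail unwritten; it does not state a rule shown to give a wrong result. Read as a whole, its default is each outcome compared by assigned arm in all who have it, with missingness described. An analyst of a two-arm randomized pilot would ordinarily work that way and show the number missing in each arm.

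The bias from the narrower reading cannot be sized from this document. It depends on how many are lost after randomization (0 to 21 of 71 on the forecast's numbers), how that loss divides between arms, and how suppression differs among those lost. It is zero if nobody is lost after randomization, or if loss is equal and those lost are alike in both arms. This conclusion assumes that analysts do not treat the recruitment forecast as an exclusion rule, and that records supply at least some outcomes for people who miss the follow-up interview. Feasibility is the pilot's main question and efficacy is declared preliminary, which also limits what hangs on the point.
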